**PROTOCOL TITLE: SMYLS: A Self-Management Program for Youth Living with Sickle Cell Disease**

**PRINCIPAL INVESTIGATOR: [name], RN**

## 1.0 Objectives / Specific Aims

### Primary Aims:

***Aim 1:** Assess feasibility of implementation processes among adolescents/caregivers, young adults, and providers including reach, enrollment, fidelity, adoption, acceptability, and satisfaction using the RE-AIM framework.*

***Aim 2:** Monitor health care activities that occur via adolescent/caregiver- or young adult-provider health communication and explore relationships between health care activities, such as provider screening, supporting, informing, and referring, and adolescent self-management behaviors, such as monitoring and tracking symptoms, attending clinic appointments, and administering home medications and treatments, and symptom outcomes.*

***Secondary Aim:** Obtain estimates of variability for measures of transition readiness, physical and psychological symptoms, healthcare utilization, and quality of life among adolescents, caregivers, and young adults.*

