### 3.0 Intervention to be studied

The web-based SMYLS app consists of three major components: patient-centered educational materials; symptom monitoring and tracking; and young adult (YA) and A/CG-provider communication. Educational materials on SCD pathophysiology, home management strategies, and symptom prevention are derived from patient-facing, guideline-based information endorsed by authoritative sources. Educational materials have been translated to an app-friendly format and are subdivided by age (up to 12 years, 12 – 17 years, adult), role (parent), or “hot” topics (hydroxyurea, research participation, hematopoietic stem cell transplantation). For symptom monitoring, pain is the predominant symptom YA and A/CG track via the app. YA and A/CG record pain scores and location via an avatar, then proceed through a series of screens to record

additional information pertaining to the pain, and additional symptoms that may co-occur. A graph is available by which YA and A/CG can observe trends in recorded pain, including specifics such as the numeric pain rating, the site of the pain, description of the pain, and actions taken to relieve pain. YA-provider or A/CG-provider communication is facilitated by a health history page intended for YA or A/CG to complete with their provider. In addition to this static option, the app also includes a link that takes the user to MyChart to complete a message to the provider via the EHR portal. Ideally, YA or A/CG will use the app daily to record and track symptoms, and as needed to access educational materials and message providers, and providers will communicate via messaging with YA or A/CG. However, a primary aim of this study is to assess participant engagement with the app. User activity and records are recorded in a secure database housed at TACHL for analysis.

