**Inclusion of Children**

Individuals included in the proposed study will include adolescents ages 11- 17 years, adult caregivers of the adolescent participants, and adult healthcare providers. A key purpose of the study is to determine the feasibility of an intervention designed to aid transition from parent/caregiver-managed to adolescent self-managed care. Therefore, adolescents with SCD and without cognitive delay that precludes ability to participate ages between the ages of 11-17 years will be included in the study.

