Data on young adult-provider or dyad-provider communication and healthcare activities will be collected via MyChart messaging. All messages between young adults and providers or dyads and providers will be retrieved as transcripts for analysis. Patients and families at the MUSC Pediatric Sickle Cell clinic do not frequently use MyChart messaging to communicate with providers and instead send text messages. To encourage use of the more secure EHR portal (MyChart) – which has the added benefit of improved provider workflow – participants will be compensated for sending messages via MyChart. Participants will be compensated with \$2 for each message with a maximum possible compensation of \$20. The number of messages sent will be tallied at the end-of-intervention (12 weeks) and provided in the form of a gift card at that time.

Data on self-management behaviors, including monitoring and tracking symptoms and administering home medications and treatments will be collected via the app and stored in the secure app database. Specifically, we will collect data on the frequency symptoms are recorded (pain, fatigue, fever, etc.) and the frequency of accessing the pain graph component of the app. We will also collect data via the app on medication adherence and recorded treatments for symptoms (drinking water, heating pad, etc.). Data on clinic appointment attendance, ED visits, and details of appointments to assess acceptability of the intervention will be obtained during weekly phone checks. Also during weekly phone checks, adolescent participants will be asked 2 – 3 questions on functioning from the PedsQL Sickle Cell Disease Module and young adult participants will be asked 2 – 3 questions on functioning from the Adult Sickle Cell Quality of Life Measurement Information System (ASCQ-Me).

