## 11.0 Data Management

**Sex as a biological variable.** We recruit equal numbers of male and female adolescents and preliminarily explore for differences by sex in outcomes, such as acceptability, satisfaction, communication content, symptoms, quality of life, transition readiness, and utilization by conducting preliminary subgroup analyses in preparation for the subsequent larger trial.

**Feasibility processes.** Variables will include those pertaining to study procedures as well as participant variables. Specifically, 95% confidence intervals for proportions will be used to estimate dichotomous outcomes including the proportion of YA, A/CG who agree to participate out of the number approached, the proportion adherent to the intervention protocol, i.e., providing daily symptom monitoring/tracking, using the education component, responding to messaging, lost to follow up, etc. For the continuous feasibility measures (length of time spent in app components), frequency distributions and the median and mean responses with 95% confidence intervals will be obtained. Benchmarks for feasibility success are recruitment rate of at least 2 YA or A/CG per week, retention rates of 70%, use of at least one component of the app  $\geq 2$  days per week (adherence), and expressed satisfaction in key informant interviews (37).

**Outcome measures and estimates of variability.** Secondary aim outcomes variables will include measures of symptoms (pain, fatigue, depression, anxiety, sleep interference), quality of life, transition readiness, and utilization (number of appointments kept, number of ED visits). Demographic and clinical variables obtained at baseline will be described via measures of central tendency (mean, median), variability and frequency distributions as appropriate. Additionally, demographic and clinical characteristics for those who adhered to the study protocol versus those who did not adhere (non-adherers and drop outs) will be compared to better describe the study population. For continuous quality of life measures, the difference between pre-and post-intervention measurements will be estimated via 95% confidence intervals. To assess preliminary intervention effects, we will conduct repeated measures ANCOVA with variables in individual models adjusting for “dose” defined as number of times each portion of the app was accessed, total time spent in each portion of the app, number of days symptoms were recorded, and number of A/CG-provider messages.

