**Content of patient-provider communication.** Our methods of analysis are modeled after the work of Goldsmith and colleagues, who created a framework of caregiver communication types from qualitative data, and subsequently used the framework as a coding structure (38, 39). We will analyze the messages between YA and providers and A/CG and providers using directed content analysis (40) and nVivo 11 (41). We will build on the work of Goldsmith (39) and of Jacob et al. (42), who applied an inductive approach to analyze text messages and developed a framework of healthcare activities that occur via text communications. According to Jacob’s framework, the two main healthcare categories are collaborating and coaching, and the four subcategories are screening, referring, informing and supporting. Jacob’s framework will serve as the initial coding framework for our analysis. Data that do not fit in any of the framework codes will be analyzed separately to identify new, additional codes. We will then conduct frequency

counts to identify the number of YA and A/CG with each type of code and the number and types of codes for each YA and A/CG. Also modeled after the work of Goldsmith and colleagues (38), we will conduct preliminary analyses to explore relationships between number and types of healthcare activities and self-management and symptom outcomes in A/CG.

**Key informant interview analyses.** Data will be analyzed using content analysis (43) and nVivo 11 (41). Analysis will be conducted in three phases. First, during preparation, the unit of analysis will be selected based on meaning, and may include a word, sentence, phrase, or paragraph. We will also immerse ourselves in the data to make sense of the whole by listening to audio recordings and reading transcripts multiple times. Second, we will organize the data using a deductive approach and the RE-AIM framework as an unconstrained coding matrix. To use an unconstrained matrix, we will apply the principles of inductive analysis to identify categories within the RE-AIM framework (43). Data will be reviewed and coded within the identified categories. Third, results will be described through the meaning of categories and subcategories. Emergent categories and subcategories will provide essential information on overall perceptions of the intervention, satisfaction, acceptability, and anticipated future use.

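### Aim 2 concerns adolescent self-management, but nothing attributes app entries or messages to the adolescent or the caregiver, so its association cannot be read as adolescent behaviour

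*Combined protocol and SAP*

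**What the plan says.** Aim 2 (section 1.0) relates provider activities to "adolescent self-management behaviors, such as monitoring and tracking symptoms, attending clinic appointments, and administering home medications and treatments" and to symptom outcomes. Under Inclusion of Children, the protocol describes an intervention "designed to aid transition from parent/caregiver-managed to adolescent self-managed care".

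The operational text mostly speaks of the pair:

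- Section 3.0: "YA and A/CG record pain scores and location via an avatar".
- Section 10.0, app data: data on "administering home medications and treatments will be collected via the app and stored in the secure app database". The user within the pair is not named.
- Section 10.0, messages: "All messages between young adults and providers or dyads and providers will be retrieved as transcripts for analysis".
- Section 11.0, outcome measures: the dose variables are "number of times each portion of the app was accessed, total time spent in each portion of the app", the days with a symptom record, and the count of messages between A/CG and provider.
- Section 11.0, communication content: codes are tallied per young adult and per A/CG. The Aim 2 analysis then examines "relationships between number and types of healthcare activities and self-management and symptom outcomes in A/CG".

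The adherence benchmark in section 11.0 (some app component used on at least 2 days a week) names no user. In Table 1, utilization, transition readiness and pain are marked as adolescent only. Symptom monitoring and tracking, under Adoption, is marked A/CG.

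**The concern.** The construct belongs to one person and the data may come from two. Both members of a dyad must own a smartphone (section 5.0), and the app carries content for parents (section 3.0). The Background says parents often take part in all of the adolescent's care, more so at younger ages, and enrolment starts at age 11. Messages are paid at $2 each up to $20, with no statement of which member must send them. Caregiver activity in the app and in MyChart is therefore foreseeable.

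If nobody records who acted, a dyad in which the caregiver does everything can produce the same counts as one in which the adolescent does everything. For a study of the move to self-management these are opposite results. The association in Aim 2, a primary aim, would carry the ambiguity, and so would the model of communication and self-management development that section 11.0 intends to build from the integrated findings. If a dyad shares one account, authorship may not be recoverable afterwards.

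**Working it through.** The plan gives no power calculation or other figure on this point to reproduce. The check has four steps.

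**1. Unit of each quantity**

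| Quantity | Source | Unit stated | Actor recorded? |
|---|---|---|---|
| Self-management (the construct) | Aim 2, section 1.0 | Adolescent | n/a |
| Symptom recording | Section 3.0 | A/CG | Not stated |
| Treatments and medication records | Section 10.0 | None; app database | Not stated |
| Clinic attendance | Section 10.0, weekly phone checks | Not an app or message count | n/a |
| Message retrieval | Section 10.0 | Dyad | Not stated |
| Message code counts | Section 11.0 | Each A/CG | Not stated |
| Message part of dose | Section 11.0 | A/CG | Not stated |
| App part of dose; adherence benchmark | Section 11.0 | None | Not stated |
| Aim 2 association | Section 11.0 | A/CG | Not stated |

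The message measures and the association are set at pair level in the text. For app use the unit is left open.

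**2. Units affected.** Section 6.0 gives 30 dyads and 15 young adults. Individuals: 30 × 2 + 15 = 75, which matches section 7.0. Of the 30 + 15 = 45 analysis units, 30/45 = 67% are dyads. The Aim 2 association is written for A/CG, so all 30 of its units are affected.

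**3. What an unattributed count can hide.** A dyad exactly at the benchmark for the whole intervention has 12 weeks × 2 days = 24 days of use. The caregiver share is not given. Over its full range of 0% to 100%, the adolescent's own days run from 24 to 0 with the same total.

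**4. Illustration for the adherence benchmark.** These assumptions are not in the documents: constant daily use probability *a* for the adolescent and *c* for the caregiver, independent between people and days, with a day counted if either uses the app.

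- Pair's daily probability: d = 1 − (1 − a)(1 − c).
- P(at least 2 of 7 days) = 1 − (1 − p)^7 − 7p(1 − p)^6, with p = a for the adolescent alone and p = d for the pair.

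For a = 0.10 alone: 1 − 0.9^7 − 7 × 0.1 × 0.9^6 = 1 − 0.478 − 0.372 = 0.15. For the pair with c = 0.1: d = 1 − 0.9 × 0.9 = 0.19, giving 0.40.

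| a | Adolescent alone | Pair, c = 0 | Pair, c = 0.1 | Pair, c = 0.2 | Pair, c = 0.5 |
|---|---|---|---|---|---|
| 0.05 | 0.04 | 0.04 | 0.27 | 0.53 | 0.95 |
| 0.10 | 0.15 | 0.15 | 0.40 | 0.63 | 0.96 |
| 0.30 | 0.67 | 0.67 | 0.80 | 0.89 | 0.99 |

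If pair-level use were read as adolescent use, the overstatement could run from nothing to very large. It is greatest where the adolescent uses the app least.

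**The case against.** The strongest reply is that the documents leave attribution unspecified; they do not state a wrong rule. Several points in it stand.

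- A reader might infer that the study cannot see the parent-to-adolescent shift at all. Table 1 does not support that. It lists the Youth and Parent Sickle Cell Responsibility Scale and adolescent-only transition readiness, with surveys at baseline, 6 weeks, 12 weeks and 3 months after the intervention. Up to 15 dyads are also interviewed about self-management development.
- A reader might infer that caregiver app entries are scored as the adolescent's by design, or that every behavioural measure is pooled. Neither is stated. No log-in arrangement is described. A/CG in Table 1 can simply mean that both people are measured, as for fatigue and depression. Section 11.0 gives each participant a unique identifier. Clinic attendance comes from phone checks.
- A reader might conclude that adherence should count adolescent use only. Caregivers are intended users, and Aim 2 itself defines the communication as adolescent/caregiver with provider. Dyad-level message codes and a dyad adherence figure are therefore legitimate.
- The work is exploratory, in a single-group feasibility study, and no comparison of young adults with dyads is planned.

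This narrows the point without removing it. Transition readiness is a secondary-aim survey, the analysis text never names the Responsibility Scale, and the interviews reach at most half of the dyads (15/30). None of these sources shows who produced the counts that enter the Aim 2 association. Message transcripts might reveal the author, but the plan does not ask for it. An exploratory association still needs its outcome to be the behaviour that the aim names.

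**Conclusion.** The point holds, limited to the app and message data. Aim 2 is about the adolescent. Message retrieval, code counts, message dose and the association are set at the level of the pair, and nothing in the text available for review attributes app entries or messages to either member. Caregiver activity can enter the counts, so the association cannot be interpreted as adolescent behaviour.

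All 30 dyads are affected. The size of any distortion cannot be derived from the documents because the caregiver share is not given. The illustrative probabilities rest on assumed, independent use rates, and the distortion vanishes if caregivers do not use the app. The conclusion rests on missing attribution and does not require that accounts are shared or that pooling is intended. It is worth settling before dyad data accumulate, since the correction is cheap and may be impossible later.

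**What to change.** 1. **Data capture (sections 3.0 and 10.0).** Record the user for each app entry, by separate log-ins or a one-tap item asking who is entering. Record the author of each MyChart message as a coding field.
2. **Aim 2 association (section 11.0, communication content).** Base the app-derived self-management measures on adolescent-made entries. Keep message codes at dyad level, as the aim defines the communication, and also tabulate them by author.
3. **Dose and adherence (section 11.0).** Report app and message counts separately for adolescent and caregiver. Report the benchmark of at least 2 days a week for the dyad and for each member.
4. **Transition.** Report the adolescent's share of dyad activity over weeks 1 to 12 descriptively, and name the Youth and Parent Sickle Cell Responsibility Scale in the analysis text.

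The cost is account set-up, one extra data field and protocol wording. Adolescent-only adherence may come out lower than the dyad figure, and the report should be ready to show both.

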**To secure data and maintain confidentiality, the following steps will be taken:**

**Participant Screening and Enrollment.** All data from participants screened for the study will be entered into an electronic REDCap study database. Designated IRB-approved research staff will collect, gather, and enter required data (written informed consent, HIPAA Authorization, and demographics) onto study data forms. Screened patients who do not meet study eligibility will have specific screening data entered into the study database. The collected data will be helpful in examining the patient population and feasibility of enrollment criteria and will include reason for exclusion. All dates will be shifted and other Personal Health Information (PHI) will be removed from the study database upon study completion. All data obtained from this study will be used for research purposes only and will comply with Federal HIPAA regulations. Master Screening and Enrollment Logs will be maintained by the PI or PC and will be used by the PI or PC to prepare reports on accrual and attrition for the SMC.

**Case Report Forms.** All proposed study specific case report forms (source documents) for data collection will be designed by the PI or PC and, when possible, transferred by the PI or PC into electronic Case Report Forms (eCRFs) for use in the study's REDCap database. These study specific eCRFs source documents (study logs for correspondence, compensation and other forms such as pre-eligibility screens) will be coded by the participant's unique study ID# for all data collected including study instruments and will be maintained in the participant research record. Completed instruments that require signature on a paper CRF will be scanned and uploaded into the study database to all for remote electronic safety monitoring as well as maintained on file in accordance with MUSC policies and applicable Federal Regulations for the Conduct of Human Participant Research.

**Binders.** The PI or PC will prepare and maintain a participant-specific binder for each participant containing all non-eCRFs records. A regulatory file will also be maintained to include the IRB-approved Protocol, original Informed Consent documents, HIPAA forms and other study-related regulatory documents. All paper research records and CRFs will be maintained in a locked file cabinet, stored in a room for research files that is accessible only via a password protected entry system that features security cameras, within the MUSC College of Nursing. Access to the research

records, study database and PHI's will be restricted to study personnel as approved by the PI and MUSC IRB. As with all studies conducted at MUSC, this study is also eligible for a random audit by MUSC Office of Compliance.

**Data Processing.** This study will use Research Electronic Data Capture (REDCap) for data capture and management. REDCap is a software toolset and workflow methodology for the electronic collection and management of research and clinical trials data. REDCap provides secure, web-based, flexible applications, including real-time validation rules with automated data type and range checks at the time of data entry. Exports are made available for several statistical packages including SPSS, SAS, SATA, R and Microsoft Excel. The study-specific REDCap electronic database will be designed and developed by the PI or PC in concert with the BS. The provision of REDCap is made available through the South Carolina Clinical & Translational Research (SCTR) Institute at MUSC with NIH Grant awards UL1RR029882 and UL1TR000062.

**Data Security.** Ensuring data security, compliance with 45 CFR 46 and maintaining the integrity of PHI is a top priority. MUSC has Standard Operating Procedures (SOP) to ensure a high level of data security while coordinating electronic and paper data management activities for clinical research trials. The REDCap study database will be hosted in the Biomedical Informatics secure data center at MUSC, a secure environment for data systems and servers on campus, and includes firewall, redundancy, failover capability, backups and extensive security checks. The secure data center has strict access control; only authorized core personnel may access the facility unescorted. Only authorized users are allowed to connect to the network, and the security of the network is actively monitored. Power and environmental controls have several layers of backups, from interruptible power supplies to alternate and redundant feeds to the local utility company. The REDCap system administrator contributes to the maintenance of institutional disaster recovery and business continuity plans. Load balancers and a highly fault tolerant SAN infrastructure contribute to high availability.

The REDCap system itself has several additional layers of protection including password protection. Access to the data and its security is managed institutionally by sponsored login IDs through a Shibboleth login with an MUSC issued NetID and features a user account management filter that controls who can access the data and to what degree. All personnel must pass an employment background check before being issued an ID. Password complexity, history and expiration standards are implemented at the institutional level. Access to individual REDCap projects and their data is managed by the owner of the project. All transactions are securely delivered to the application using Secure Sockets Layer (SSL – SHA-1 with RSA Encryption; 2048-bits). It is then transmitted internally (behind the firewall) to the database server. All transactions are logged at the server layer (httpd logging), application layers (REDCap logs activity to a database table), and the database layer, using both query and binary logging. This feature provides audit trails for all changes, queries, data exports and reports. MUSC Information security policies are available at: <https://mainweb-v.musc.edu/security/policy/>

**Data Entry.** Only MUSC IRB approved study personnel that are authorized to have access to the REDCap study database will be granted password access. Study personnel using computers that are connected to the Internet will directly enter data into the remotely housed database. As such, no electronic study data will be stored on hard drives and/or any portable electronic devices. Additionally, all personnel with access to the database will have current University of Miami CITI training in the Conduct of Human Subject Protections, and HIPAA and Information Security trainings that are completed annually. Each participant will be assigned a unique study identifier, all PHIs will be masked, and data exports will be limited to the PI, the mentor, the PC, or the BS for generating reports and the conduct of statistical data analysis.

**Data Monitoring.** Ongoing quality control procedures will be implemented for data collection, storage and processing. The PI or PC will conduct monthly monitoring of the study database and generate a report for review at team meetings. Standing agenda items for these meetings will include participant recruitment and retention, AE's, protocol deviations, data integrity and overall study conduct. The PI and PC will work to resolve and validate discrepant data. Discrepancies that warrant clarification will be sent to appropriate parties for review and resolution. All data entry and changes made in the study database by authorized study personnel will be automatically logged by REDCap, and provide a transparent visible audit trail for reviewers.

